Subcutaneous Injection of Botulinum Toxin A for At-Level Back Pain in Patients  
with Spinal Cord Injury

PI: [name]

NCT02736890

Document Date: 12/29/2015

"Data analysis plan:

The primary outcome measure used to determine treatment effect in this study was patient reported average pain intensity over the prior week. This measure is part of the International SCI Pain Basic Data Set (ISCIPBDS), whose validity and utility in individuals with SCI has been demonstrated, and is also among the measures recommended for use in SCI clinical trials. Subjects were asked to rate their average pain using the 0-10 NPRS with endpoints of 0 ("no pain") to 10 ("worst pain imaginable"). Secondary outcome measures included other items from the ISCIPBDS such as the degree to which pain interfered with: (1) day to day activities, (2) mood, and (3) sleep, all on 0-10 numeric scales with endpoints of 0 ("no interference") to 10 ("extreme interference"). At each follow-up time point, subjects were also asked to quantify the change in quality of life appreciated after injections on a 0-6 numeric scale based on the Patient Global Impression of Change (PGIC) scale. Our adaptation of this scale had endpoints of 0 ("no change, or condition got worse") to 6 ("a great deal better, a considerable improvement that has made all the difference"). Lastly, subjects were asked about and monitored for any AEs.

All collected research data were stored in a password-protected REDCap database and all hard copy forms were kept in locked files in the offices of research staff. Statistical analyses were performed using SPSS version 22.0. Power analyses were conducted based on the primary outcome of change in pain intensity on the NPRS from baseline. We determined that a minimal clinical important difference (MCID) on the NPRS would be  $\geq 3$  points on the 0-10 point scale, that 30% of participants in the placebo group would have a positive response to treatment, and that 40% more participants (i.e. 70%) would respond in the treatment group. Assuming a two-sided alpha of 0.05, a sample size of 28 would have provided 86% power that a difference will be found. Assuming a 15% drop out rate, a sample size of 32 enrolled participants was deemed necessary for sufficient power to detect treatment effect. Our study failed to meet this target sample size and it was ultimately determined that our findings would be best presented as a descriptive case series."

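### Does scoring no change and worsening alike as 0 on the adapted PGIC item require a change to the plan?

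*SAP*

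**What the plan says.** The relevant text is in the SAP under Data analysis plan, where the outcome measures are listed. At each follow-up, "subjects were also asked to quantify the change in quality of life appreciated after injections on a 0-6 numeric scale". The next sentence defines the scale. For the lower end it says "Our adaptation of this scale had endpoints of 0 ('no change, or condition got worse", and the upper end is "6 ('a great deal better, a considerable improvement that has made all the difference". The SAP mentions no companion question that would split score 0.

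The same paragraph lists the other outcomes. The primary one is average pain over the prior week: "Subjects were asked to rate their average pain using the 0-10 NPRS with endpoints of 0 ('no pain') to 10 ('worst pain imaginable". The secondary ones include "the degree to which pain interfered with: (1) day to day activities, (2) mood, and (3) sleep", also on 0-10 scales. On safety it adds: "Lastly, subjects were asked about and monitored for any AEs".

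The following paragraph ties the sample size to pain and not to the PGIC item: "Power analyses were conducted based on the primary outcome of change in pain intensity on the NPRS from baseline". It closes by saying that the target sample size was not met and that "our findings would be best presented as a descriptive case series". The SAP names no mean, median, distribution or test for the PGIC item, and none for the interference items.

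**The concern.** The label and the anchors do not quite match. An item said to quantify change would normally be expected to move both ways. This one has no score for getting worse: everything above 0 is improvement, and 0 covers both stability and any degree of decline.

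If a mean of these scores were reported and taken as the average change in quality of life, it could not be negative, whatever happened to the participants. Within a group the error could only be upward. In a small series with no planned test behind it, the label and the chosen summary carry much of the interpretation, so a favourable mean could hide participants who deteriorated. Because the SAP states no summary for the item, nothing in its text expressly rules this reading out.

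**Working it through.** The SAP gives no figure for this item, so there is nothing to reproduce. The check has two parts: how large the distortion could be, and whether following the SAP would produce it.

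**1. Size of the floor effect.** Let X be a participant's true net change, with negative values meaning worse. The item records max(X, 0). Then

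recorded mean − net mean = (share worse) × (average worsening among those worse).

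An example with assumed values, six participants in each series:

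- Series A: +3, +3, 0, 0, 0, 0. Net mean 6/6 = +1.0. Recorded mean 6/6 = 1.0. Shift 0.
- Series B: +3, +3, −3, −3, −3, −3. Net mean (6 − 12)/6 = −1.0. Recorded mean 6/6 = 1.0. Shift (4/6) × 3 = 2.0.

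The recorded scores are identical, so the item alone cannot separate the two series.

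The SAP does not give the share who worsened. Assuming 0 to 30% worse, by 1 to 3 points on average, the shift runs from 0 to 0.3 × 3 = 0.9 points.

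A normal model for X with mean m and SD s, ignoring rounding and the ceiling at 6, gives

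E[max(X, 0)] = m·Φ(m/s) + s·φ(m/s), with share worse Φ(−m/s).

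For m = 1 and s = 2: 1 × 0.691 + 2 × 0.352 = 1.396, a shift of 0.40. Each cell below shows the shift, then the implied share worse:

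| Net mean m | s = 1 | s = 2 | s = 3 |
|---|---|---|---|
| 0 | 0.40 (50%) | 0.80 (50%) | 1.20 (50%) |
| 1 | 0.08 (16%) | 0.40 (31%) | 0.76 (37%) |
| 2 | 0.01 (2%) | 0.17 (16%) | 0.45 (25%) |

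Rounding X to whole points and limiting it to −6 to 6, with SD 2, hardly matters: net means of −1, 0 and +1 are recorded as about 0.39, 0.79 and 1.38.

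The large shifts need a large share of deteriorating participants. Five of the nine cells imply more than 30% worse, and the largest, 1.20, implies half. A normal distribution with SD 3 is also a crude model for a 0-6 item. The table shows how the shift behaves and does not estimate it for this trial.

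**2. Direction in a comparison.** If results were shown by group with equal spread, the floor would shrink a difference. With s = 2, a true difference of 1 (means 0 and 1) is recorded as 1.396 − 0.798 = 0.598. For means 1 and 2 it is 2.167 − 1.396 = 0.771. Under that assumption, benefit over placebo is understated.

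**3. Does following the SAP produce the error?** Two steps are needed: someone reports a mean, and someone reads it as net change.

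- The SAP plans no mean for the item. The descriptive presentation it adopts fits individual scores or counts at each score.
- The SAP does not speak of net change. It gives the meaning of 0 in the sentence right after the item is introduced.
- Worsening can show on the pain scale and the three interference scales as a rise from any baseline below 10, and adverse events are collected separately.

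**The case for a change.** The strongest case for a change is that this is a mismatch between two adjacent statements, not an omission that the protocol might fill. The item is called a measure of change and its anchors make it a measure of improvement. The correction would be cheap and still possible after data collection: relabel the item, tabulate the count at each score from 0 to 6, and list the pain, interference and adverse-event data for those scoring 0. Those other outcomes also do not restore the direction of the global item, because a participant may feel worse overall without a higher pain score.

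Much of this stands. Score 0 does merge two states, the item cannot show harm, and the other outcomes give context without replacing it. What does not stand is the step from there to a defect. The anchors are disclosed where the item is defined, so the label misleads only a reader who skips the next sentence. The absence of a named summary is not peculiar to this item and is easily filled in a descriptive report. The proposed listing would pick participants by their outcome and still not show who felt worse overall. Nor can the adaptation be faulted for the merged anchor, since the SAP does not say whether it came from the source scale.

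**Conclusion.** No change to the plan follows. The observation is correct, but it limits how one secondary item should be read and does not make any stated method wrong. The distortion arises only if a mean is reported and taken as net change. Its size is then the share worse times the average worsening: 0 if nobody worsened, and up to 0.9 points under the assumed limits of 30% and 3 points. The SAP contains no data to narrow that range.

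The primary outcome and the sample-size reasoning do not use the item. An analyst working from the printed anchors would treat it as degree of improvement, with 0 meaning unchanged or worse, and would give the number of participants at each score at each follow-up. Writing that into the SAP would record sensible practice but could not separate the zeros, because the answers were collected on this scale.

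### Does the plan commit to comparing treatment with placebo on NPRS change without adjusting for baseline pain?

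*SAP*

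**What the plan says.** The SAP has one relevant section, the Data analysis plan. It names the outcome first: "The primary outcome measure used to determine treatment effect in this study was patient reported average pain intensity over the prior week", scored on the 0-10 NPRS. Turning to sample size, it says "Power analyses were conducted based on the primary outcome of change in pain intensity on the NPRS from baseline".

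The inputs to that calculation follow. "We determined that a minimal clinical important difference (MCID) on the NPRS would be" at least 3 points. For the control arm it is assumed that "30% of participants in the placebo group would have a positive response to treatment"; the rate assumed on active treatment is 70%, which is 40 percentage points higher. The test is two-sided at the 5% level, and the stated result is that "a sample size of 28 would have provided 86% power that a difference will be found". The enrolment target is then set: "Assuming a 15% drop out rate, a sample size of 32 enrolled participants was deemed necessary".

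On method, the section names only the software, SPSS 22.0. It gives no test, model, covariate or estimator. Its last sentence says that the target sample size was not reached and that the findings would be presented as a descriptive case series.

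**The concern.** Taken together, the outcome, the power sentence and the 3-point threshold seem to define treatment effect in two ways only: raw change, and a fixed drop. Both depend on where a patient starts. By regression to the mean, patients with high baseline pain tend to fall further and pass a fixed threshold more often, whatever the treatment. In small groups the arms will differ at baseline by chance, and part of that difference enters an unadjusted comparison. Baseline NPRS has to be collected anyway to compute change, so adjustment would need no new data.

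If the plan did prescribe such a comparison, the price would be a noisier treatment estimate than the same data could give.

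**Working it through.** **1. The plan's own figure.** Inputs from the Data analysis plan: 30% versus 70% responders, two-sided alpha 0.05. Assumed: two parallel arms of n each, pooled two-proportion test.

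Power = Φ[(0.40 − 1.96·√(2·0.5·0.5/n)) / √((0.3·0.7 + 0.7·0.3)/n)]

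- n = 28 per arm: (0.40 − 1.96·0.1336)/0.1225 = 1.13, power 87.0%, close to the stated 86%.
- n = 14 per arm (28 in total): (0.40 − 1.96·0.1890)/0.1732 = 0.17, power 56.8%.

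Two things follow. The calculation compares proportions and uses no NPRS standard deviation or baseline correlation, so it does not reveal how a mean change would be analysed, and baseline adjustment would not alter it. The SAP also does not say whether 28 is a total or a per-arm number, so a group size of 14 is an assumption. Which reading was meant is a separate question.

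**2. What adjustment could gain.** The SAP gives no SD and no baseline-to-follow-up correlation ρ. Assume an equal SD σ at both times and ρ from 0.3 to 0.7. Per patient, the variance of raw change is 2σ²(1−ρ) and the residual variance after adjustment is σ²(1−ρ²). The ratio is (1+ρ)/2:

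- ρ = 0.3: 0.65, so raw change has 1/0.65 = 1.54 times the variance.
- ρ = 0.5: 0.75, so 1.33 times.
- ρ = 0.7: 0.85, so 1.18 times.

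At 14 per group, simulated ratios of 95% interval width (adjusted to raw change) are about 0.82, 0.88 and 0.94.

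**3. What chance imbalance does.** The standard error of the baseline mean difference is σ√(2/n), and a share (1−ρ) of any imbalance passes into raw change. With σ = 2 and ρ = 0.5, a 1-SE imbalance shifts the change difference by 0.5·2·√(2/14) = 0.38 points at 14 per group, and by 0.5·2·√(2/8) = 0.50 at 8 per group.

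For the 3-point threshold, the SD of change is 2·√(2·0.5) = 2, and a 30% placebo response implies a mean fall of 3 − 0.524·2 = 1.95. Given baseline, the residual SD is 2·√0.75 = 1.73. The chance of a drop of 3 or more is then 0.12, 0.27 and 0.49 at 1 SD below, at, and 1 SD above mean baseline.

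This is the same loss as in step 2. Since (1−ρ²) + (1−ρ)² = 2(1−ρ), the extra variance of raw change is exactly the imbalance term. Under randomisation it is random error, already reflected in the unadjusted interval, and not bias.

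**4. Very small groups.** Adjustment costs one degree of freedom and a term for the observed imbalance. At 4 per group and ρ = 0.7 the expected width ratio is the product of √0.85 = 0.922, the t-quantile ratio 2.571/2.447 = 1.051, about 0.99 for the residual SD and about 1.10 for the imbalance term, which is about 1.06. At 5 per group simulation gives 1.01. Adjustment then widens the interval slightly. The SAP does not say how many patients were enrolled.

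**5. Does the SAP prescribe the unadjusted analysis?** The three statements the concern rests on are an outcome definition, a power statement and a threshold used for power. None is an analysis rule. Nor does the word change settle the matter: regressing change on treatment and baseline gives the same treatment coefficient as regressing the follow-up score on treatment and baseline, because subtracting baseline alters only the baseline slope, from β to β − 1.

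**6. Is there a contrast left to adjust?** The closing sentence replaces the planned comparison with descriptive reporting. The SAP does not say that a treatment-versus-placebo estimate will still be shown, even as exploratory.

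**The case for a change.** The strongest opposing case is that a section headed as an analysis plan should fix the analysis, and that the only operational definitions in it subtract baseline without conditioning on it. A reader left to fill the gap would probably run a test on change scores or compare responder proportions. The statistics behind the concern are sound: the variance ratio is standard, and at 14 per group adjustment helps across the assumed range of ρ. If someone does set the arms side by side in the case series, smaller groups make chance imbalance larger.

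What stands is that no analysis model is named. That is an absence of detail, which the protocol may supply and which is not at hand here. It is not a wrong choice made in this document. The rest depends on a between-group estimate that the SAP no longer promises. Asking for an adjusted mean difference with a 95% interval would put a model-based contrast back into a study that missed its target and turned to description. It would also make the responder proportion secondary, although the 30%, 70%, 28 and 86% figures rest on it. The argument further presumes parallel arms; the reference to a placebo group suggests them, but the document does not state the design.

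**Conclusion.** The concern does not hold. The SAP does not say that treatment effect will be judged on unadjusted change; that reading is inferred from the power paragraph. As it ends, the plan reports no treatment-versus-placebo estimate, so baseline adjustment has nothing to improve.

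The possible gain, intervals about 6% to 18% narrower at 14 per group, is real only for a comparison that has been dropped. It also assumes two parallel groups of that size, equal SDs and ρ between 0.3 and 0.7, none of which the SAP states. At 4 or 5 per group with ρ = 0.7 the gain becomes a small loss, about 6% and 1%. No change is called for on this point.

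### For two independent groups, the stated 86% power needs 28 per group; 28 in total gives about 57%, yet 28 is inflated directly to 32 enrolled participants

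*SAP*

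**What the plan says.** The power calculation is in the second paragraph of the Data analysis plan in the SAP. A responder is defined by a change of at least 3 points on the 0-10 pain scale. For the control arm the assumption reads "30% of participants in the placebo group would have a positive response to treatment". The active arm is assumed to do better by 40 percentage points: "40% more participants (i.e. 70%) would respond in the treatment group". The error rate is set by "Assuming a two-sided alpha of 0.05".

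The result is that "a sample size of 28 would have provided 86% power that a difference will be found". The next sentence carries this number to enrolment: "Assuming a 15% drop out rate, a sample size of 32 enrolled participants was deemed necessary for sufficient power to detect treatment effect".

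The paragraph ends by reporting that "Our study failed to meet this target sample size" and that "our findings would be best presented as a descriptive case series".

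The SAP does not label 28 or 32 as per group or total. It also gives no allocation ratio and names no test for this calculation.

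**The concern.** The wording describes two groups and a comparison of two proportions. For that comparison, 28 is a familiar per-group number at about 86% power. The dropout step, however, treats the same 28 as the whole trial: it is inflated once, and the result is given as enrolled participants, which reads most naturally as a trial total. It looks as if a per-group sample size was carried forward as a total.

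If so, the planned trial was about half the size that its stated power required. The shortfall reported in the last sentence would then be measured against a target that could not have delivered that power.

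**Working it through.** **Inputs.** All from the SAP, Data analysis plan, second paragraph: p1 = 0.30, p2 = 0.70, difference 0.40, two-sided alpha 0.05 (z = 1.96), stated size 28, stated power 86%, dropout 15%, stated enrolment 32. Two independent groups of equal size is an assumption; unequal splits and a paired design are checked below.

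**Formula (pooled z, n per group).** With mean proportion 0.50:

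- SE0 = √(2 × 0.50 × 0.50 / n) = √(0.50 / n)
- SE1 = √((0.30 × 0.70 + 0.70 × 0.30) / n) = √(0.42 / n)
- Power = Φ((0.40 − 1.96 × SE0) / SE1)

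**Step 1. Reproduce the 86% with 28 per group.** SE0 = 0.1336 and SE1 = 0.1225, so power = Φ((0.40 − 0.2619) / 0.1225) = Φ(1.13) = 87.0%. Enumerating the uncorrected chi-square test over all outcomes gives 86.1%. The plan's figure is reproduced.

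**Step 2. Read 28 as the total, 14 per group.** SE0 = 0.1890 and SE1 = 0.1732, so power = Φ((0.40 − 0.3704) / 0.1732) = Φ(0.17) = 56.8%.

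**Step 3. Other methods, other splits, and all 32 evaluable.**

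| Method | 28 per group | 28 total, 14/14 | 28 total, best split | 32 total, 16/16 | 32 total, best split |
|---|---|---|---|---|---|
| Pooled z | 87.0% | 56.8% | 56.8% (14/14) | 62.9% | 62.9% (16/16) |
| Unpooled z | 90.4% | 63.7% | 63.7% (14/14) | 69.5% | 69.5% (16/16) |
| Arcsine | 86.9% | 58.6% | 58.6% (14/14) | 64.4% | 64.4% (16/16) |
| Chi-square, enumerated | 86.1% | 54.4% | 58.9% (12/16) | 64.7% | 64.9% (14/18) |
| Fisher exact | 79.0% | 39.9% | 49.3% (10/18) | 49.6% | 56.4% (15/17) |

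Best split means the highest power over every division of the total into two groups. No method and no split of 28, or even of 32, comes near 86%. A one-sided 0.05 test, which is not what the SAP states, would give only about 70% at 14 per group (pooled z).

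**Step 4. The dropout step.** 28 × 1.15 = 32.2 and 28 / 0.85 = 32.9, so 32 comes from inflating 28 itself. The difference between 32 and 33 is rounding or convention and is not at issue. If 28 is per group, there are two ways to state the total:

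- Doubling the SAP's 32 gives 64 enrolled. Then 32 × 0.85 = 27.2, and 27 per group has 85.7% power (pooled z).
- Dividing by the retention rate gives 56 / 0.85 = 65.9, so 66 enrolled.

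Either is about twice the stated 32.

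**Step 5. Paired design (an assumption, not in the SAP).** Let p01 be the proportion responding on placebo only, so that p10 = p01 + 0.40 respond on active treatment only. If a patient's two responses are independent, p01 = 0.30 × 0.30 = 0.09. McNemar power with 28 pairs, by enumeration:

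| p01 | Uncorrected | Exact |
|---|---|---|
| 0.05 | 91.8% | 87.2% |
| 0.09 | 85.3% | 79.2% |
| 0.15 | 76.7% | 68.3% |

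Values of p01 above 0.09 imply negative correlation between a patient's own responses, so the lower end of this range rests on an unusual assumption.

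**The case against.** The strongest reply is that the error exists under only one of three readings.

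- If 28 and 32 are both per group, the calculation is right and only those two words are missing.
- If every participant was to receive both treatments, 28 participants, 32 enrolled and 86% can hold together. With zero or positive within-patient correlation, uncorrected McNemar power is at least 85%.
- Only if 28 is the total across two independent groups is 86% wrong.

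The protocol, which is not at hand, may state the design and allocation. The trial also missed its target whether that was 32, 64 or 66.

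Much of this stands: the conclusion is conditional on the design, and the consequence is small. The absence of a design statement or allocation ratio is not itself the finding. But the SAP states the power, the size and the enrolment target together, and it speaks of a placebo group and a treatment group. It mentions no pairing and no discordant proportions, and it gives 32 simply as enrolled participants. On that wording, the two-group total is the natural reading, and under it the figures conflict. The per-group reading rescues the power only by doubling an enrolment figure that the SAP never says is per group.

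**Conclusion.** The point holds as a minor one. For two independent groups, 30% versus 70%, two-sided 0.05, the 86% belongs to 28 per group. With 28 in total the power is about 57% by pooled z, roughly 29 points lower than stated (86 − 57), and 40% to 64% across the five methods at equal allocation. A total of 32, all evaluable, would still give only about 63% by pooled z and at most 69.5% by any method or split examined.

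The two-group arithmetic is certain. That the design was two independent groups, and that 32 is a trial total, is likely from the wording but not stated. Severity is low because the study is reported descriptively. What is affected is the public account of how far the trial fell short of a size adequate for its stated power.

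**What to change.** Check the design first. Then label 28 as per group, total or pairs, and name the test behind the 86%.

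If the design was two parallel groups, keep the 86% as the planning record and add a note beside it, for example:

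> For 30% versus 70% responders (two-sided 0.05, pooled normal approximation), 28 evaluable participants in total (14 per group) give about 57% power. The planned 86% needs 28 per group, that is 56 evaluable and about 66 enrolled at 15% dropout.

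Describe the shortfall in the last sentence against that number.

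If the design was paired, replace the two-group wording with a McNemar calculation that states the assumed discordant proportions.

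The cost is wording only, with no further enrolment and no re-analysis. Under the two-group reading, the stated power for 28 in total becomes less favourable.

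### Does an enrolment target of 32 fall short of the 28 evaluable participants once 15% drop out?

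*SAP*

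**What the plan says.** The sample-size reasoning is in the second paragraph of the SAP's data analysis plan. A responder threshold of at least 3 points on the 0–10 NPRS is set, with assumed response rates of 30% on placebo ("30% of participants in the placebo group would have a positive response to treatment") and 70% on treatment ("40% more participants (i.e. 70%) would respond in the treatment group"). At a two-sided alpha of 0.05, the SAP states that "a sample size of 28 would have provided 86% power that a difference will be found". It then adds the allowance for loss: "Assuming a 15% drop out rate, a sample size of 32 enrolled participants was deemed necessary".

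No inflation formula or rounding rule is given, and neither 28 nor 32 is labelled as a total or a per-group number. The paragraph closes by reporting that the target was not reached and that the findings were therefore presented descriptively, as a case series.

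**The concern.** A dropout rate applies to the people enrolled, so the usual inflation divides the evaluable number by one minus the rate. Here that is 28/0.85 = 32.94, or 33 when rounded up. The SAP has 32. Multiplying 28 by 1.15 gives 32.2, which is 32 to the nearest whole number, so the figure looks like the familiar slip of adding 15% to the evaluable number instead of dividing by 0.85.

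If so, the enrolment target does not deliver the evaluable number behind the stated power, under the SAP's own dropout assumption. The same slip applied to 28 per group would give 56 × 1.15 = 64.4, or 64 in total, against 56/0.85 = 65.9, or 66.

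**Working it through.** **Inputs, all from the SAP's power paragraph:** 28 participants for 86% power; response rates 0.30 and 0.70; two-sided alpha 0.05; 15% dropout; 32 enrolled. Equal allocation to two parallel groups is my assumption.

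**1. The stated power.** I used the normal approximation for two proportions with n per group, pooled variance under the null and unpooled under the alternative:

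power = Φ{[0.40 − 1.96·√(2 × 0.5 × 0.5/n)] / √[(0.3 × 0.7 + 0.7 × 0.3)/n]}

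- n = 28 per group: (0.40 − 1.96 × 0.1336)/0.1225 = 1.127, power 87.0%. The arcsine version gives 86.9%. Both are within about a point of the stated 86%.
- n = 14 per group (28 in total): (0.40 − 1.96 × 0.1890)/0.1732 = 0.171, power 56.8%. This does not reproduce 86%.

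**2. The enrolment figure.**

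| Calculation | Result | Nearest | Up | Truncated |
|---|---|---|---|---|
| 28/0.85 | 32.94 | 33 | 33 | 32 |
| 28 × 1.15 | 32.2 | 32 | 33 | 32 |

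The stated 32 is reached by the correct formula truncated, or by the incorrect one rounded to nearest or truncated. Rounded up, both formulas give 33. The number alone does not show which route was taken.

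**3. What 32 delivers.** 32 × 0.85 = 27.2, against 33 × 0.85 = 28.05. In whole people, four losses from 32 (4/32 = 12.5%) leave exactly 28, and five (5/32 = 15.6%) leave 27. The assumed 15% lies between these two outcomes.

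**4. What the missing participant costs.**

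| Reading of 28 | Power at 28 | Power after the shortfall |
|---|---|---|
| Per group | 87.0% | 86.0% at 27.2 per group; 85.7% at 27 |
| Total, two groups | 56.8% (14 per group) | 55.1% at 13.5 per group |

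On the per-group reading the loss is 87.0 − 85.7 = 1.3 points, and the result still rounds to 86%. On the total reading it is 56.8 − 55.1 = 1.7 points, from a figure already far below 86%. Comparing 13 with 14 per group (53.5% with 56.8%) would overstate the cost, because that drops two participants, not one.

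**The case for a change.** The strongest case for a correction is that the three figures 28, 15% and 32 cannot all hold, whichever way 28 is read and whatever formula was used. An enrolment target meant to secure 28 should be rounded up, and rounding up gives 33 by either route. If each participant drops out independently with probability 0.15, the chance that 32 enrolled yields at least 28 completers is about 46%, against about 63% for 33 (binomial). The document is public, its sample-size paragraph could be reused in planning a later trial, and the correction is a single number.

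The inconsistency stands: 32 is one short. The attribution to a 1.15 multiplier does not, since the SAP shows no formula. The completer probabilities are correct but set a test the plan does not: the SAP ties 32 to sufficient power, not to a guaranteed count of 28, and power barely moves between 27 and 28 per group. As for reuse, anyone borrowing this paragraph would first have to settle whether 28 is a total or a per-group number. That changes the target from 33 to 66, and settling it means recalculating the dropout allowance anyway.

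**Conclusion.** The arithmetic observation is right and small: at 15% dropout, 32 enrolled leaves about 27 evaluable, one short of 28. Whether this comes from the formula or from rounding cannot be determined from the SAP.

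There is no gain in changing it. If 28 is per group, the stated 86% survives the shortfall (85.7% at 27). If 28 is a total in a two-group parallel comparison, the stated power is unsupported before any dropout; that is a separate question about labelling, and this step neither causes nor cures it. The study missed its target and was presented descriptively, so whether the unmet target was 32 or 33 bears on no estimate, test or conclusion.

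The power figures assume equal allocation to two parallel groups and the normal approximation. A paired design, which this document does not state, would give different values: for 28 in total, 83.2% if responses are independent and up to 96.3% at the lowest possible discordance. Independent responses at 27 give 81.7%, so the cost of one participant there is also small, at 83.2 − 81.7 = 1.5 points.
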